13.3 Audit and inspection

The study is conducted under the responsibility of the sponsor in compliance with the applicable international and local regulatory requirements as well as applicable ICH guidelines, Helsinki Declaration (1996) and in respect of the sponsor and/or CRO SOPs for study conduct and monitoring.

Audits may be carried out by the Sponsor/CRO representatives, and inspection may be performed by regulatory authorities' inspectorate before, during, or after the study. The investigator will allow and assist the CRO/sponsor's representatives and any regulatory agency to have direct access to all study records, CRFs, subject medical records, study drug dispensing records and study drug storage area, study facilities, and any other documents considered source documentation.

For the Audit(s) performed by, or on behalf of, sponsor auditors, audit certificate(s) will be provided to the investigator.

13.4 Quality Control and Insurance

In order to ensure the conformity of the studies entrusted to Good Clinical Practices and regulatory requirements, DERMSCAN has implemented a quality management system which has been certified ISO 9001:2008.

This system consists of procedures and quality controls.

13.5 Final Report

A final report according to ICH E3 will be written by the Laboratoires Théa.

This final report will be signed by the Coordinating Investigator, the Biostatistician and the Sponsor.

13.6 Insurance

The sponsor has subscribed an insurance contract to cover the liability of the investigators, the sponsor himself and anyone involved in the study.

The copy of the insurance certificate is presented separately in the EC and CA submission file.

13.7 Publications policy

The sponsor reserves the right to review all the manuscript(s) and abstract(s) before their submission for publication or presentation. Publication of data will be at the discretion of the sponsor

This is not intended to restrict or hinder publication or presentation, but to allow the sponsor to protect proprietary information and to provide comments based on information that may not yet be available to the investigator(s).

14 ETHICS CONSIDERATIONS

Declaration of HELSINKI⁽¹⁾

The current revision of the Declaration of Helsinki is the accepted basis for clinical study ethics, and must be fully followed and respected by all engaged in research on human beings. Any exceptions must be justified and stated in the protocol. Independent assurance that patients are protected can only be provided by an ethics committee/institutional review board and freely obtained informed consent.

Good Clinical Practice⁽²⁾

Good clinical practice is a standard for clinical studies, which encompasses the design, conduct, monitoring, termination, audit, analyses, reporting and documentation of the studies. It ensures the studies are ethically justified and scientifically sound, and that the clinical properties of the diagnostic/therapeutic/prophylactic product under investigation are properly documented.

It is the responsibility of the investigator(s) to ensure that the study is performed in accordance with the international Good Clinical Practice standards and according to all local laws and regulations concerning clinical studies.

Ethics Committee and Competent Authority⁽³⁾

It is the responsibility of the sponsor or its legal representative to submit a copy of the protocol and detailed patient information sheet and consent form to an ethics committee/institutional review board in order to obtain independent approval to conduct the study. Ethics committee/institutional review board approval

must be obtained before the study is started. The approval of the ethics committee/institutional review board must be sent in writing, to the sponsor or its legal representative. The Ethics Committee approval letter must mention the Ethics Committee members and their function.

In parallel or after the Ethics Committee submission, the sponsor or its legal representative must address an authorization request to the Tunisian authorities.

Any clinical trial cannot be performed without having obtained the agreement of the Ethics Committee and the inherent authorization of the Tunisian authority.

Appendix 1: MCMONNIES SCALE

- Case Report Form (CRF) final version 1.0 dated on 06-DEC-2017,

The analyses closely follow the ICH guidelines for industry on topic E3 - Structure and Content of Clinical Study Reports and E9 - Statistical Principles for Clinical Trials.

Any changes from the planned analyses will be described and justified in the clinical study report.

1 DESCRIPTION OF THE STUDY

1.1 Study objectives

1.1.1 Primary objective

The primary objective is to assess the efficacy of T2769 in patients with moderate to severe Dry Eye Syndrome.

1.1.2 Secondary objective(s)

The secondary objective is to assess safety of T2769.

1.2 Study design

1.2.1 Description

This is a study in open, non-comparative, multicentre, on ambulatory patients.

1.2.2 Schedule of assessments and study procedures

All patients were expected to attend four visits during the course of the investigation as presented below:

- Visit#1: Screening visit Day -14/D-10.
- Visit#2: Day 1.
- Visit#3: Day 14 (+/- 1 day).
- Visit #4 - Final Visit: Day 42 (+/-5 days).

FLOW CHART: Study investigations were to be conducted as per the following schedule of study procedures:

Study procedure	Screening visit Visit# 1 D-14/D-10	Run-in Period	Inclusion visit Visit# 2 D1	Visit# 3 Day 14 (+/- 1 day)	Final Visit Visit# 4 Day 42 (+/- 5 days) Or withdrawal visit
Informed consent	X	Preservative free artificial tears (NaCl 0.9%)			
Demographic information	X				
Ocular and systemic medical and surgical history	X				
Previous and concomitant ocular and systemic treatments	X		X	X	X
History of Dry Eye	X				
Symptomatology evaluation (Visual Analog Scale [VAS])	X		X	X	X
Ocular symptoms	X		X	X	X
Ocular symptoms upon instillation			X	X	X
Soothing sensation within 15 min after IP instillation				X	X
Far Best Corrected Visual Acuity in both eyes	X				X
Ocular Surface Disease Index (OSDI) score			X	X	X
Schirmer test			X	X	X
Slit Lamp examination					
Tear Break up Time (TBUT)	X		X	X	X
Oxford 0-15 grading scheme Scale	X		X	X	X
Van Bijsterveld staining	X		X	X	X
Conjunctival hyperaemia (Mac Monnies photographic scale)	X		X	X	X
Auxiliary product dispensation	X				
Auxiliary product compliance			X		
Investigational product dispensation			X	X	
Investigational product compliance				X	X
Adverse events			X	X	X
Ocular efficacy assessment by the investigator				X	X
Ocular tolerance assessment by the investigator				X	X
Ocular tolerance assessment by the patient				X	X

1.3 Study endpoints

1.3.1 Primary efficacy endpoint

The primary efficacy endpoint is the evolution of the ocular symptomatology on a Visual Analog Scale (VAS) between D1 and after 42 days of treatment (D42).

1.3.2 Secondary efficacy endpoints

The secondary efficacy endpoints are:

- Evolution of global ocular staining score according to Oxford 0-15 grading scheme (fluorescein coloration) between Day 1 (D1) and after 42 days of treatment (Day 42 [D42]),
- Evolution of Van Bijsterveld score (lissamine green coloration) between D1 and after 42 days of treatment (D42),
- Soothing sensation assessed by the patient at D42.

1.3.3 Other efficacy endpoints

1.3.3.1 Other evaluation parameters at D14

The other efficacy criteria at D14 are:

- Evolution of the ocular symptomatology on a VAS between D1 and after 14 days of treatment (D14),
- Evolution of global ocular staining according to Oxford 0-15 grading scheme (fluorescein coloration) between D1 and after 14 days of treatment (D14),
- Evolution of Van Bijsterveld score (lissamine green coloration) between D1 and after 14 days of treatment (D14),
- Soothing sensation assessed by the patient at D14.

1.3.3.2 Other evaluation parameters at D14 and D42

The other efficacy criteria at D14 and D42 are:

- Evolution of Ocular Surface Disease Index (OSDI) score after 14 days (D14) and 42 days of treatment (D42).
- Evolution of the following Dry Eye symptoms after 14 days (D14) and 42 days of treatment (D42): burning/irritation, stinging/eye pain, itching/pruritus, eye dryness feeling, foreign body sensation, tearing, light sensitivity graded by the patient.
- Evolution of conjunctival hyperaemia at slit lamp examination after 14 days (D14) and 42 days of treatment (D42).
- Evolution of Schirmer test (without anaesthesia) after 14 days (D14) and 42 days of treatment (D42).
- Evolution of Tear Break-Up Time (TBUT) after 14 days (D14) and 42 days of treatment (D42).
- Ocular efficacy assessment by the investigator using a 4-point verbal scale at D14 and D42.

1.3.4 Safety endpoints

Safety assessment criteria are:

- Ocular symptoms upon instillation including burning/irritation, stinging/eye pain, itching/pruritus, eye dryness feeling, foreign body sensation, and other symptoms graded by the patient after 14 days and 42 days of treatment with the T2769
- Far best corrected visual acuity (FBCVA) after 42 days of treatment with the T2769,
- Ocular tolerance assessment by the investigator after 42 days of treatment with the T2769,
- Ocular tolerance assessment by the patient after 42 days of treatment with the T2769,

- Ocular and Systemic Adverse Events (AEs) recorded throughout the investigation by the investigator.

1.4 Study treatments

1.4.1 Treatment groups

Each patient was instructed to instill the IP T2769 for 42 days, one drop in each eye, 3 to 6 times daily.

1.4.2 Randomisation

1.4.2.1 Randomisation procedure

Not Applicable.

1.4.2.2 Masking

Not Applicable.

1.5 Sample size considerations

The primary efficacy criterion is the change from baseline in ocular symptoms at D42 assessed using a VAS. Assuming that the mean change is 12, the standard deviation (SD) is 23, the correlation between pairs is 0.4, a total of 50 evaluable patients achieves a power of at least 90% (calculated power = 91%) for the two-sided test for no difference with a normal distribution and a significance level of 5%.

Fixed Scenario Elements	
Distribution	Normal
Method	Exact
Number of Sides	2
Alpha	0.05
Mean Difference	-12
Standard Deviation	23
Correlation	0.4
Number of Pairs	50
Null Difference	0
Computed Power	0.910

A total of 55 patients should be enrolled in the study to take into account approximately 10% of non-evaluable patients. Estimates of the mean, SD and correlation between pairs are based upon data of previous studies (Laboratoires THEA. Clinical study LT2762-PIV-11/13, 2017) SAS 9.4 was used for the sample size calculation (POWER procedure, PAIRED MEANS statement).

2 ANALYSIS SETS

The following analysis sets will be considered.

2.1 Safety set

The Safety set will include all enrolled patients having received at least one dose of the IP. The Safety set will be the primary population for the safety analysis.

Note: Enrolled patients will be patients who have signed the informed consent and for whom the screening visit (D-10) has been recorded in the CRF.

2.2 Modified intent-to-treat set

The modified intent-to-treat (mITT) set will include all enrolled patients having received at least one dose of the IP and with at least one baseline and post-baseline efficacy assessment. mITT set will be the primary population for the efficacy analysis.

2.3 Per-protocol set

The Per-protocol (PP) set will include all mITT patients without any major violation of clinical investigational procedures. Deviations from the protocol including violations of inclusion/exclusion criteria will be detailed in a separate document and assessed as “minor” or “major” in cooperation with the sponsor during a blind review meeting prior to the database lock. PP set will be considered as a secondary population and will be used for sensitivity analyses.

3 GENERAL CONSIDERATIONS FOR DATA ANALYSES

Statistical analyses will be performed by the Biostatistics unit of AIXIAL. Analyses will be conducted with SAS® software, version 9.4 (SAS Institute, North Caroline, USA).

All tables will present the result for the overall population.

Quantitative variables (Continious data) will be summarized in summary tables indicating the number of non-missing observations (n), mean, SD, median, lower quartile (Q1), upper quartile (Q3), minimum and maximum, and 95% Confidence Interval (CI) of the mean/median.

Qualitative variables (Categorical data) will be summarized in summary tables indicating the number of non-missing observations (n), count and percentage of each modality, and 95% CI.

95% CI of a proportion will be calculated using the score method of Wilson without continuity correction:

$$\text{Lower Limit} = \frac{2np + z^2 - z\sqrt{z^2 + 4npq}}{2(n + z^2)} \quad \text{Upper Limit} = \frac{2np + z^2 + z\sqrt{z^2 + 4npq}}{2(n + z^2)}$$

With n = number of non-missing observations

p = percentage

q = 1 – p

z = 1.96 for two-sided 95%CI

Except minimum and maximum, descriptive statistics will be presented with one more decimal than the recorded value.

For all variables, the number of missing values will also be reported in the tables, but they will not be counted for the percentage calculation (categorical data).

Variables recorded for each eye will be described separately for the worse eye and for the other eye (if applicable).

An eye is eligible if it respects the inclusion criteria without exclusion criteria (ophtalmological criteria) at screening visit and inclusion visit.

The worse eye is defined as:

- For patients with both eligible eyes:
 - Eye with the worse Oxford score (higher value);
 - if same Oxford score in both eyes: eye with the worse Schirmer score (lower value);
 - if same Oxford and Schirmer scores in both eyes: eye with the worse TBUT score (lower value);
 - if same Oxford, Schirmer and TBUT scores in both eyes: right eye.
- For patients with one eligible eye: eligible eye.
- For patients with both not eligible eyes:
 - Eye with the worse Oxford score in the range ≥ 4 and ≤ 9 ;
 - if same Oxford score in both eyes: eye with the worse Schirmer score in the range ≥ 3 and ≤ 9 mm/5min;
 - if same Oxford and Schirmer scores in both eyes: eye with the worse TBUT ≤ 30 seconds;
 - if same Oxford, Schirmer and TBUT scores in both eyes: or no eye in the range for these 3 criteria right eye.

The acceptable risk of error for the statistical tests will be set at 5%.

Quantitative parameters will be compared between visits using paired t-test. Assumptions underlying the Student test will be checked:

- Kolmogorov-Smirnov test will be performed to check the assumption of normality,
- Normal probability plot ≤ QQ-plot will be performed to check the assumption of normality,

If there is a strong violation of normality assumption, in addition to the initial model, a Signed rank test will be performed.

For centre effect, primary endpoint will be compared between centre using Analysis of Variance (ANOVA). Assumptions underlying the ANOVA for the sensitivity analyses will be checked:

- Kolmogorov-Smirnov test will be performed to check the assumption of normality,
- Normal probability plot and QQ-plot will be performed to check the assumption of normality,
- Levene's test will also be performed to check the homogeneity of variances.

If there is a strong violation of homogeneity of variances or normality assumption, in addition to the initial model, a Kruskal-Wallis test will be performed.

A document will be provided to summarize normality.

3.1 Display of analysis results

Following labelling will be used in statistical tables: "T2769" (single group) or "TUN001" / "TUN002" / "TUN003" and "Total" (by centre).

3.2 Interim analyses

No interim analysis will be performed.

3.3 Centre effect management

Centre effect will be tested by ANOVA for the primary endpoint (Section 6.1.3).

3.4 Subgroup analyses

The primary efficacy criterion and secondary criteria will be described by centre.

3.5 Other strata and covariates

Not Applicable.

3.6 Multiple comparisons and multiplicity

There is a single primary efficacy endpoint in the study (comparaison of symptomatology evaluation between D1 and D42). Other efficacy measures are defined to be of secondary importance. Thus comparison will be performed at a two-sided significance level of 0.05; no adjustment of the type I error rate will be made.

4 DATA HANDLING CONVENTIONS

4.1 Visit windows

All data will be recorded and organised according to the scheduled visits outlined in the protocol. However, actual observation times may differ from the scheduled visit times and where this occurs the results should be allocated to the most appropriate visit.

Therefore, time intervals (e.g. visit windows) have been constructed so that every observation collected after D1 can be allocated to a particular time point. If more than one record occurs within the same visit window where only one assessment is expected then the following rule should be applied: the closest non-missing result to the scheduled visit should be used.

Scheduled visit post baseline	Time interval (days)
Follow-up visit (D14+/-1)	1 to 27 days
Final visit (D42+/-5)	28 to 55 days
Time interval (days): Date of visit – Date of inclusion visit (D1)	

Moreover, last visits recorded more than 24h after the last instillation will not be considered in the analysis.

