4.2 Premature discontinuation and missing data

If a patient is prematurely withdrawn from the study for any reason, the investigator must make every effort to perform the evaluations described for the D42 visit.

In the mITT set, missing values will be imputed using the last observation available on treatment method (LOCF).

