6.1.1 Main analysis of the primary efficacy endpoint

To assess the efficacy of T2769, on change in ocular symptomatology assessed on a VAS between D1 and D42, estimate of the change and associated 95% CI will be provided, as well as p-value for the paired t-test on the mITT set. Based on the LOCF method, missing values will be replaced by the last available value.

The syntax with SAS using the UNIVARIATE procedure is detailed in APPENDIX 1.

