7.2 FBCVA

FBCVA will be summarised at screening visit and D42 using usual descriptive statistics for continuous variable, in Log Mar. Frequency distribution in classes (i.e., values from 1/10 to 10/10 and $> 10/10$, with non-integer numbers rounded to the nearest integer) will be also presented.

FBCVA will be presented by worse and contralateral eye separately.

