7.3 Ocular tolerance assessment by the investigator

Ocular tolerance by the investigator assessed on a 4-point ordinal scale (Very satisfactory / Satisfactory / Not very satisfactory / Unsatisfactory) will be presented by frequency distribution for each modality and frequency distribution after regrouping 'very satisfactory' with 'satisfactory', and 'not very satisfactory' with 'unsatisfactory'.

Ocular tolerance assessment will be described at each assessment time (D14 and D42).

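### SAP 4.1 makes no exception for the withdrawal visit, so safety findings from withdrawals before day 28 can miss every summary table, and the source of the carried-forward VAS is left open

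*SAP*

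**What the plan says.** SAP 4.1 builds its windows "so that every observation collected after D1 can be allocated to a particular time point". Days are counted as visit date minus D1 date: 1 to 27 is the follow-up (D14) visit and 28 to 55 is the final (D42) visit. Where a window holds more than one record and one is expected, "the closest non-missing result to the scheduled visit should be used". A separate sentence adds that "last visits recorded more than 24h after the last instillation will not be considered in the analysis".

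On withdrawal, SAP 4.2 repeats protocol 6.6.2.1: "the investigator must make every effort to perform the evaluations described for the D42 visit". The flow charts in both documents head the Visit 4 column as Day 42 or withdrawal visit.

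On missing data, SAP 4.2 states LOCF for the mITT set only, taking the last on-treatment observation. For the primary endpoint SAP 6.1.1 says: "Based on the LOCF method, missing values will be replaced by the last available value". Safety endpoints are analysed on the Safety set (SAP 7), for which no imputation is stated, and missing values are left out of percentages (SAP 3).

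On time points, "FBCVA will be summarised at screening visit and D42" (SAP 7.2). Tolerance and instillation symptoms are summarised at D14 and D42 (SAP 7.1, 7.3 and 7.4).

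**The concern.** The plan collects an end-of-treatment assessment at withdrawal and then relabels it by date. A patient who attends Visit 3 and withdraws on day 21 has two records in the D14 window and none in the D42 window, and only one of the two is used. Worsening dryness, lack of efficacy and adverse events are among the withdrawal reasons in protocol 6.6.2.1, so some of the displaced records may come from patients for whom the product did badly.

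Safety is the study's secondary objective and there is no control arm. Which measured safety data reach the tables therefore matters. For the primary endpoint, two programmers following the same SAP could carry forward different VAS values.

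**Working it through.** **Inputs.** Windows, closest-record rule and 24 h rule: SAP 4.1. Visit 3 allowed at D14 ± 1 day: flow chart. FBCVA measured only at screening and at Visit 4/withdrawal: flow chart and protocol 9.1.2. LOCF scope: SAP 4.2 and 6.1.1. Planned change 12 mm, SD 23, correlation 0.4, 50 evaluable, 55 enrolled: SAP 1.5.

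**The plan's own figure.** SD of the paired difference = 23 × √(2 × (1 − 0.4)) = 25.20. The exact two-sided paired t-test with 50 pairs and a 12 mm change has power 0.910, as stated. This point does not alter the sample size; 12 mm serves below only as a yardstick.

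**Which withdrawal records are displaced.** Study Day 14 can be read as 13 or 14 elapsed days, so both were tried, with Visit 3 one day early, on target or one day late.

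| Target (elapsed days) | Visit 3 attended | Withdrawal days displaced by Visit 3 |
|---|---|---|
| 13 | 12 | 15–27 (13 days) |
| 13 | 13 | 14–27 (14 days) |
| 13 | 14 | 15–27 (13 days) |
| 14 | 13 | 16–27 (12 days) |
| 14 | 14 | 15–27 (13 days) |
| 14 | 15 | 16–27 (12 days) |

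The only exceptions arise when Visit 3 is a day early. A withdrawal on the target day then replaces Visit 3, and one on the day after the target ties with it. SAP 4.1 gives no rule for ties.

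**What happens to each endpoint (withdrawal visit within 24 h of the last drop).**

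| Withdrawal visit | VAS | Tolerance, instillation symptoms | FBCVA |
|---|---|---|---|
| Before Visit 3 | Only record in window; kept and carried to D42 | Kept, tabulated at D14 | Labelled D14; no such row |
| After Visit 3, before day 28 | Depends on LOCF source | Displaced; in neither D14 nor D42 summary | Labelled D14; no such row |
| Days 28–55 | In the D42 window | In the D42 window | In the D42 window |

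FBCVA is not measured at Visit 3, so the closest-record rule does not remove it. It is lost because a D14 label has no place in Tables 5.7 and 5.8. The displaced instillation record is not a duplicate: protocol 9.1.4 asks about the period since the previous visit, so it is the only account of the time from Visit 3 to withdrawal. Appendix 2 plans no individual listing of FBCVA or tolerance, and Listing 5.1 covers only other instillation symptoms.

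**VAS, if LOCF uses windowed records.** With k patients withdrawing after Visit 3 and before day 28, each d mm worse at withdrawal than at D14, the overstatement of mean improvement is k × d / N. The documents give neither k nor d. Assumed values, N = 55:

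- k = 1, d = 10: 10/55 = 0.2 mm
- k = 3, d = 20: 60/55 = 1.1 mm
- k = 5, d = 20: 100/55 = 1.8 mm
- k = 5, d = 30: 150/55 = 2.7 mm, or 2.73/12 = 23% of the planned change

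If LOCF uses all on-treatment records, the overstatement is 0.

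**The case against.** *LOCF can be read literally.* The last on-treatment value for a patient seen on days 14 and 21 is the day-21 value, and no sentence restricts LOCF to window-selected records. This stands. A reader might infer that the withdrawal VAS is certainly lost from the primary analysis, and the documents do not support that. They do not exclude it either: disposition and Listing 1.2 work with visits as considered in the analysis, and the table shell has only D14, D42 and D42-LOCF rows after baseline. The observed-data sensitivity analysis on the mITT set would not show the difference, because such a patient has no D42 record.

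*SAP 4.1 leaves some room.* It speaks of the most appropriate visit, limits the closest-record rule to cases where one assessment is expected, and the flow chart equates Visit 4 with withdrawal. A programmer might file the withdrawal visit under Visit 4 on that basis. But the text goes on to define allocation by elapsed days for every record, with no stated exception.

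*Safety signals survive elsewhere.* Worsening of the condition is an adverse event by definition (protocol 9.3.1.1), and adverse events are not windowed. Events leading to withdrawal and discontinuation reasons are tabulated, with a listing of the reasons. This stands, and it limits the harm to the FBCVA, tolerance and instillation summaries.

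*The sizes are assumed.* A reader might infer a demonstrated bias in the product's favour. Patients may also withdraw at their own request or for other reasons, so the direction is not fixed. The allowance of about 10% in SAP 1.5 is for non-evaluable patients. It is not a forecast of withdrawals between Visit 3 and day 28, and a patient with a D14 value is evaluable under LOCF.

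**Conclusion.** The concern holds in three parts.

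- **FBCVA:** under SAP 4.1 and 7.2 as written, every value from an on-treatment withdrawal visit before day 28 is absent from Tables 5.7 and 5.8.
- **Tolerance and instillation symptoms:** ratings from withdrawals after Visit 3 and before day 28 are displaced on nearly every possible day, and nothing in the Safety set restores them.
- **Primary VAS:** the defect is an ambiguity. Its effect is zero on one reading and k × d / N on the other, from 0.2 mm to 2.7 mm over the assumed range. The top of that range needs five withdrawals in about two weeks, each 30 mm worse and each seen within 24 h of the last drop.

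It would be wrong to say that all withdrawal data before day 28 drop out. A patient who withdraws before Visit 3 loses only FBCVA. Visits more than 24 h after the last instillation are excluded by a different sentence, whatever the windows say.

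**What to change.** 1. In SAP 4.1, exempt the withdrawal visit from the date windows and the closest-record rule, and keep it as the end-of-treatment record.
2. In SAP 4.2 and 6.1.1, state that LOCF carries the chronologically last on-treatment value, taken before windowing. The secondary and other efficacy endpoints in SAP 6.2 and 6.3 also rely on LOCF and would follow.
3. In the Safety-set tables for FBCVA, tolerance and instillation symptoms, add a row for D42 or withdrawal (last on-treatment assessment), beside the existing D42 row.

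This costs SAP wording, one row in a few tables and a small change to the visit-allocation program. No new data are needed. The drawback is that the new row mixes treatment durations, so it should be labelled as such and should not replace the D42 row.

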9.1.2 Far best-corrected visual acuity in both eye

Far Best-corrected visual acuity will be measured at the screening visit (visit #1) and on Day 42 visits with the patient's best correction using a Snellen chart.

The value at screening visit will be the baseline value.

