5 DESCRIPTION OF THE STUDY POPULATION

5.1 Disposition of patients

The number of enrolled patients will be presented. The number (%) of patients included in each analysis set (Safety, mITT and PP sets) will be presented. The number (%) of patients by centre will be presented for each analysis set.

The number (%) of patients per visit as considered in the analysis will be described on the Safety set, on the mITT set and for the PP set.

The number (%) of patients who prematurely discontinued the study and the primary reason for discontinuation will be presented on the Safety set and on the mITT set. A listing will be performed presenting the patients who prematurely discontinued the study with the detailed reason for discontinuation.

The number (%) of patients with at least one major deviation, the number (%) of patients with only minor deviations (without major deviations) and the number (%) of patients with minor deviations (including those with major deviations) will be presented on the mITT set. The reasons for deviation will be also described on the mITT sets and an individual patient data listing with all minor/major deviations will be provided.

A listing of all the patients including information about populations and reason for exclusion, worse eye, will be performed on the enrolled patients' population.

A listing of visits as considered in the analysis will be performed on the enrolled patient's population.

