6.1.2 Sensitivity analysis of the primary efficacy endpoint

Sensitivity analysis will be performed without replacement of missing values on the mITT and PP sets.

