7 SAFETY ANALYSIS

Safety endpoints will be analysed on the Safety set.

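### SAP 4.1 drops last visits made more than 24 h after the last instillation without limiting the rule to efficacy, and no planned analysis shows what it does to the primary VAS change

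*SAP*

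**What the plan says.** - **The rule.** After the table of visit windows, SAP 4.1 adds that "last visits recorded more than 24h after the last instillation will not be considered in the analysis". It does not say which analysis. The windows assign days 1 to 27 to D14 and days 28 to 55 to D42. If a window holds more than one record, the one closest to the scheduled visit is used.
- **Withdrawal visits.** SAP 4.2 says that after premature withdrawal for any reason "the investigator must make every effort to perform the evaluations described for the D42 visit"; protocol 6.6.2.1 says the same. The SAP 1.2.2 flow chart heads the last column "Final Visit Visit# 4 Day 42 (+/- 5 days) Or withdrawal visit".
- **Safety.** SAP 7 says "Safety endpoints will be analysed on the Safety set" and sets no visit rule of its own. SAP 5.1 says that the number of "patients per visit as considered in the analysis will be described on the Safety set", as well as on the mITT and PP sets.
- **FBCVA.** Protocol 9.1.2: "Far Best-corrected visual acuity will be measured at the screening visit (visit #1) and on Day 42 visits". SAP 7.2: "FBCVA will be summarised at screening visit and D42".
- **Efficacy.** Protocol 12.1 and SAP 4.2 specify LOCF from the last on-treatment observation in the mITT set. Protocol 12.2 also requires an on-treatment efficacy assessment for m-ITT membership; SAP 2.2 leaves those words out.
- **Sensitivity analysis.** SAP 6.1.2: "Sensitivity analysis will be performed without replacement of missing values on the mITT and PP sets".
- **Declaration.** The 24 h limit is not in protocol section 12 and not in the list of changes in SAP section 8.

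**The concern.** Sites are asked to collect a full set of D42 evaluations from patients who stop early, and the SAP then discards that visit if it came more than 24 h after the last drop. Protocol 6.6.2.1 lists adverse events, worsening and lack of efficacy among the reasons for withdrawal, and protocol 7.5.3 allows the product to be interrupted for an adverse reaction. A gap of more than 24 h is therefore plausible in patients whose final acuity and tolerance are most informative.

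Two things are at stake. A programmer who follows the text would apply an on-treatment filter to Safety-set summaries, although the protocol defines that set by one dose of product only. And for the primary VAS change, an earlier value may replace a later one with no estimate of the effect. The direction cannot be read from the documents: late values may be worse, or better if other treatment had been started.

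**Working it through.** **1. Does the rule reach the Safety set?** SAP 4.1 has no qualifier, whereas the LOCF sentence in SAP 4.2 is expressly limited to the mITT set. SAP 5.1 and Table 1.6 apply the notion of visits as considered in the analysis to the Safety set, and SAP 7 does not override it. On the wording, it does.

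**2. Which safety data does it remove?**
- *AEs:* none need be lost. SAP 7.5 selects treatment-emergent events by onset date, with no upper limit.
- *FBCVA, last visit on days 28 to 55:* lost because of the 24 h rule, with no other post-baseline value.
- *FBCVA, withdrawal on days 1 to 27:* assigned to D14, while SAP 7.2 reports only screening and D42 and LOCF is specified for the mITT set only. It misses the D42 summary with or without the rule.
- *Tolerance and instillation symptoms:* reported at D14 and D42, so a late last visit on days 28 to 55 loses its ratings. On days 1 to 27 the rule decides the matter only if that window has no record closer to schedule. Ratings from a separate D14 visit remain.

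**3. Does any planned analysis lift the rule?** No. SAP 6.1.2 removes the imputation and SAP 6.1.3 tests centre; both keep the exclusion. Tables 1.6 to 1.8 and Listings 1.2 and 1.3 help trace the visits but re-estimate nothing.

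**4. The plan's own figure.** Inputs from SAP 1.5: mean change 12 mm, SD 23, correlation 0.4, 50 pairs, two-sided 5%.
- SD of change = 23 × √(2 × (1 − 0.4)) = 25.195
- SE = 25.195/√50 = 3.563; 12/3.563 = 3.37, p = 0.0015
- Exact paired-t power with 49 df = 0.910, as stated. It is not in dispute.

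**5. Possible shift in the primary mean.** Assumptions, not in the documents: k = 1 to 5 of 50 patients affected; d = discarded minus carried change, between −12 and +24 mm. Restoring the values moves the mean change by k × d/50, to be compared with the planned −12 mm.
- k = 1: −0.24 to +0.48 mm
- k = 5: −1.2 to +2.4 mm

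A positive figure means that the reported result was too favourable by that amount.

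**6. Effect on the test at the planned 12 mm**, with the carried values placed at −12 mm and replaced by −12 + d:
- k = 5, d = +24: mean −9.6. Sum of squares = 49 × 25.195² + 45 × 2.4² + 5 × 21.6²; SD 26.22; SE 26.22/√50 = 3.709; t = 2.589; p = 0.013; 95% CI −17.1 to −2.1.
- k = 1, d = +24: mean −11.52, p = 0.0024.
- k = 5, d = −12: mean −13.2, p = 0.0006.

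Suppose instead that the five carried changes were 0 (no improvement) and the restored ones +24. The other 45 then average −600/45 = −13.33, and their sum of squares about that mean is 49 × 25.195² − 5 × 12² − 45 × 1.333² = 30,305. About the new mean of −9.6 the total is 30,305 + 45 × 3.733² + 5 × 33.6² = 36,577; SD 27.32; t = 2.485; p = 0.016.

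**7. When would significance be lost?** The smallest significant reported change is 2.0096 × 3.563 = 7.16 mm. With k = 5, d = +24 and carried values at the mean, the reported improvement must exceed 2.4 + 2.0096 × 3.709 = 9.85 mm. Under these extremes only a reported improvement of about 7.2 to 9.9 mm would lose significance.

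**8. A case outside this calculation.** A patient whose only post-baseline visit was late has no on-treatment value to carry. SAP 2.2 as worded may keep that patient in the mITT set; protocol 12.2 would not.

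**The case against.** The strongest reply is that the rule only makes the protocol's on-treatment principle operational. Protocol section 12 leaves detailed methods to the SAP, and 24 h is a reasonable cut-off for a product instilled 3 to 6 times daily; a patient still on treatment at the visit would not trigger it. That stands for efficacy. A reader might infer that SAP 4.1 contradicts the protocol or that the primary analysis is wrong, but protocol 12.1 and 12.2 support the opposite. The request there is for an added estimate.

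It can also be said that the safety tables concerned are descriptive, that the study is an open pilot, and that the sponsor may have meant efficacy only. The first two limit the consequences. The third is possible, but the text does not say so.

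A further reply is that the FBCVA loss comes partly from the visit windows. That is correct. With 1 to 5 of 55 patients affected, it is tempting to say that D42 FBCVA falls to 54 to 50 patients because of the 24 h rule. The documents do not support that, since withdrawals on days 1 to 27 miss the D42 summary regardless. Exempting safety from the rule would therefore not be enough.

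Finally, the counts and differences are assumed, and the range is wider in the direction unfavourable to the product. That is so; they serve only to bound the effect.

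**Conclusion.** The point holds in limited form. For safety, SAP 4.1 as written extends an on-treatment filter to the Safety set without a basis in the protocol. For efficacy, the cut-off is defensible, but its influence on the primary result is never shown.

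On size, the documents do not give the number of late last visits. Under the assumed 1 to 5 of 50 patients and −12 to +24 mm, the reported mean is off by at most 1.2 mm against or 2.4 mm in favour of T2769, and at the planned 12 mm the test stays significant. This supposes that each affected patient has a value to carry forward.

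Two stronger inferences should be resisted. The rule does not hide adverse events, because those tables follow onset dates. Nor does its absence from SAP section 8 show an intention to favour the product: for efficacy it can be read as a detail of a principle already in the protocol, and the direction of its effect is unknown. The reading of the text is firm; the practical impact is uncertain and probably modest.

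**What to change.** 1. **SAP 4.1 and 7.2.** Limit the 24 h rule to efficacy analyses and state that Safety-set summaries use all recorded visits. In 7.2, add a summary of the last recorded post-baseline FBCVA, including withdrawal visits on days 1 to 27. Without that addition, lifting the rule leaves the early withdrawals out.
2. **SAP 6.1.2.** Add one sensitivity analysis of the primary VAS change that uses the final or withdrawal-visit value whatever the time since the last instillation. Run it in all treated patients with a baseline and any post-baseline VAS. An mITT set restricted to on-treatment assessments would drop patients whose only post-baseline visit was late. Flag values taken after other treatment was started, and report how many visits the 24 h rule excludes.
3. **Minor wording.** List the rule in SAP section 8. Align SAP 2.2 and 6.1.1 with the on-treatment wording of SAP 4.2 and protocol 12.2.

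The cost is a few sentences and one or two extra tables from evaluations the protocol already asks for. The downside is that the sensitivity estimate may be less or more favourable than the primary one, and the report must then explain the difference.
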